Short term effect of smoking cessation on human metabolism

Authors: [name], [name] and [name]

Helsinki Committee approval number (Meuhedet HCO, Israel): 05-23-03-16

Date of the approval: 14/4/2016.

Date of beginning of recruitment: 18/4/2016

METHODS

The trial was designed as a two-arm study - prospective and retrospective. The study was approved by the Meuhedet HMO Ethics Committee according to the ethical guidelines of the Helsinki Committee.

Prospective Arm

Studied population

The prospective arm included 108 participants aged 30-70 who were recruited from the smoking cessation workshops of the Meuhedet HMO (Israeli Health Services) during 2016-2017. Candidates with benign tumors, bariatric surgeries, and endoscopic bariatric procedures before or during the study period were excluded.

Study design

All subjects signed informed consent to participate, after receiving detailed information about the study objectives and procedure. The collected data included weight, BMI, waist circumference and Waist Hip Ratio (WHR) at 3 time points: a. the third weekly meeting of the cessation workshop, pre-cessation phase (baseline- **phase 0**), b. workshop's last meeting (the eighth weekly cessation meeting – **phase 1**) and 6 months after the cessation program (**phase 2**). The effects of smoking cessation support medicines was also examined.

Anthropometric measurements

Weight was measured with participants standing up, wearing light clothes and without shoes, using a digital scale. Waist circumference was measured above

the iliac crest. Hip circumference was taken at the maximum circumference between the groin and the iliac crest. Height data were based on participants' self-report. Participants were classified as smokers (S), quitters (Q) and resmokers "relapsers" (RS) based on self-reported data at each visit. Participants also completed a questionnaire regarding cigarette-smoking habits and health information. The numerical value of pack years was calculated based on that questionnaire (Pack years is a unit quantifying the lifetime exposure to smoking, calculated by multiplying the number of packs of cigarettes smoked per day by the number of years the person has smoked).

Retrospective Arm

Studied population

The retrospective arm presented a file review of 200 patients between 25-70 years of age, who participated in smoking cessation workshops of the Meuhedet HMO in 2014.

Candidates with benign tumors, bariatric surgeries, and endoscopic bariatric procedures before or during the study period were excluded, as well as those who were unavailable for a phone conversation.

Study design

Two blood test results, as documented in medical files, were collected and analyzed. The first one during the year preceding the smoking cessation workshops (baseline- **phase 0**), and the second during the year after completing them. Smoking status was verified by a telephone call. Participants were classified as smokers (S) and quitters (Q). The effect of smoking cessation medications on metabolic profile was also examined.

Metabolic measurements

File recorded blood measurements were used for Fasting Glucose (BFG), Total Cholesterol (TC), HDL Cholesterol (HDL), LDL Cholesterol (LDL) and triglycerides (TG) as examined in HMO laboratories. Results were analyzed according to WHO criteria.

STATISTICAL ANALYSIS

Data was analyzed using JMP Pro 12 and R software. Mean values and their standard error (SE) were used to summarize the distribution of continuous variables. To determine significant statistical differences between two sets of data with normal distribution we used Student's t-test/ ANOVA. For paired sets of data that may not be normally distributed we used the Wilcoxon signed rank test, and for unmatched sets-, the Mann Whitney's u-test was used. Each patient constituted his own control – each post workshop result was compared with the pre workshop result.

Fisher's proportion test was used to determine significant statistical differences between proportions in a given compatible groups. P<0.05 was considered significant. All statistical tests were two tailed.

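### Prospective arm: pack-years are calculated but given no role in the analysis, so comparisons of smokers, quitters and relapsers may be confounded by prior smoking exposure

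*Combined protocol and SAP*

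**What the plan says.** All references are to the combined protocol and SAP.

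- **Prospective Arm, Studied population:** "The prospective arm included 108 participants aged 30-70". No sample-size derivation or group sizes are given.
- **Prospective Arm, Anthropometric measurements:** "Participants were classified as smokers (S), quitters (Q) and resmokers 'relapsers' (RS) based on self-reported data at each visit". A questionnaire covers smoking habits and health information, and "The numerical value of pack years was calculated based on that questionnaire". The text defines pack-years as a measure of lifetime exposure but does not say what they are for.
- **Statistical Analysis:** "To determine significant statistical differences between two sets of data with normal distribution we used Student's t-test/ ANOVA". For data that may not be normal, paired sets get the Wilcoxon signed rank test, and "for unmatched sets-, the Mann Whitney's u-test was used". Proportions get Fisher's test. Each participant serves as their own control, after-workshop against before-workshop. The threshold is P<0.05, two-sided.

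Pack-years do not appear in the Statistical Analysis section, and neither does any adjusted model. The section does not say how smokers (S), quitters (Q) and relapsers (RS) are compared, whether on change or on level, or which visit's status defines the group.

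**The concern.** Membership of S, Q or RS is an outcome of each participant's own behaviour, not of allocation. Lifetime exposure could plausibly be related both to the chance of quitting and to how weight or waist changes afterwards. If both relations exist, a crude Q-versus-S or Q-versus-RS difference mixes the effect of quitting with that of having been a lighter or heavier smoker.

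The between-group contrast matters because a change within quitters alone cannot separate cessation from time, the workshop or the support medicines. Attributing the change to cessation needs a comparison group, and the only tests the plan offers for that are unadjusted. Here the candidate confounder has been measured, so leaving it out is an avoidable weakness.

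**Working it through.** **What can be reproduced.** The document gives no effect size, SD, group sizes or power, so there is no stated figure to reproduce. What follows is an illustration.

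**Inputs**
- From the document: N = 108; two-sided alpha 0.05.
- Assumed: two groups, split 50/50 or 30/70; within-group correlation of pack-years with the change, rho = 0 to 0.3; gap in mean pack-years between groups, d = 0 to 0.8 SD.

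**Formulas** (in SD units of the within-person change)
- Bias of the unadjusted difference: b = rho × d.
- SE = sqrt(1/n1 + 1/n2). At 54/54 this is sqrt(2/54) = 0.192; at 30/70 (32.4 and 75.6) it is 0.210.
- Probability of a significant result when quitting has no effect: Phi(b/SE − 1.96) + Phi(−b/SE − 1.96).

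| rho | d | b (SD) | Type I error, 50/50 | Type I error, 30/70 |
|---|---|---|---|---|
| 0 | any | 0 | 5.0% | 5.0% |
| any | 0 | 0 | 5.0% | 5.0% |
| 0.1 | 0.5 | 0.05 | 5.8% | 5.7% |
| 0.2 | 0.5 | 0.10 | 8.2% | 7.6% |
| 0.3 | 0.5 | 0.15 | 12.2% | 11.0% |
| 0.3 | 0.8 | 0.24 | 23.9% | 20.8% |

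Worked line: b = 0.3 × 0.5 = 0.15; b/SE = 0.15/0.192 = 0.78; Phi(−1.18) + Phi(−2.74) = 0.119 + 0.003 = 0.122.

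**Simulation** (4,000 runs, 54 versus 54, no true effect of quitting)

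| Scenario | Difference in change, unadjusted | Type I error, unadjusted | Difference in follow-up level | Difference in change, adjusted for pack-years | Type I error, adjusted |
|---|---|---|---|---|---|
| Pack-years affect level only (slope 0.5), d 0.5 | −0.001 | 4.8% | 0.251 | 0.000 | 4.4% |
| Also affect change (rho 0.3), d 0.5 | 0.150 | 12.2% | 0.400 | 0.000 | 4.9% |
| Also affect change (rho 0.3), d 0.8 | 0.236 | 22.3% | 0.634 | −0.001 | 4.4% |
| Also affect change (rho 0.3), d 0 | 0.004 | 5.2% | 0.008 | 0.003 | 4.7% |

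The first row shows what the own-control design achieves: a stable effect on level cancels in the change, though it reappears (0.25 SD) if follow-up levels are compared. The next two rows show what it does not achieve: confounding of the change passes straight through.

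**On the kilogram scale** (all assumed). A gap of 5 to 10 pack-years and a slope of 0.02 to 0.05 kg per pack-year give 5 × 0.02 = 0.1 kg to 10 × 0.05 = 0.5 kg. With an SD of weight change of 3 to 5 kg, the SE at 54/54 is 3 × 0.192 = 0.58 to 5 × 0.192 = 0.96 kg. The bias is then 0.1/0.96 = 0.1 to 0.5/0.58 = 0.9 of one SE.

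**Precision.** Take an assumed SD of 20 pack-years and 4 kg for the change. The same slopes imply correlations of 0.02 × 20/4 = 0.10 to 0.05 × 20/4 = 0.25, which multiply the residual SD by sqrt(1 − 0.10²) = 0.995 to sqrt(1 − 0.25²) = 0.968. Gaps of 0.25 to 0.5 SD multiply the SE by sqrt(1 + d²/4) = 1.008 to 1.031. Low slope with low gap gives a net SE ratio of about 1.003, and high with high about 0.998. Crossing them gives 0.995 × 1.031 = 1.026 and 0.968 × 1.008 = 0.976. There is no dependable gain.

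**The case against.** The strongest reply has four parts.

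1. **The only comparison the plan spells out is within person.** It uses the baseline value and removes stable differences between lighter and heavier smokers. This stands, and it limits the point. What remains is confounding of the change, or of levels if those are compared.
2. **The S/Q/RS contrast is inferred.** No sentence says how the groups are compared. This stands too. However, the plan names groups and unpaired tests, and every test it lists is unadjusted, so an unadjusted contrast is the natural reading.
3. **The magnitudes are all assumed.** This stands. The kilogram illustration stays below one SE; the correlation-based one reaches larger errors only at the top of its range.
4. **Adjustment has limits.** Sex is not described as collected, age appears only as an eligibility range, and age overlaps with pack-years. Status is reassessed at each visit, so covariates do not settle who belongs to which group. These points shape the remedy but do not remove the need for it.

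A reader might infer that exposure differences do bias the cessation effect. The document does not support that. Bias needs both a pack-years gap between groups and an association of pack-years with the change, and neither is reported. A reader might also extend the point to the blood results of the retrospective arm, but pack-years are described only for the prospective arm.

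**Conclusion.** The point holds for the prospective arm. A measured potential confounder has no stated role, every named test is unadjusted, and the groups are self-selected, so between-group results may be confounded by prior exposure. The own-control comparison answers part of this, not all.

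Size and direction are unknown. Under the assumptions shown, bias is between 0 and 0.24 SD of the change, and type I error between 5.0% and 23.9% with equal groups. Real pairwise groups may be smaller than 54, since there are three statuses. That would leave the bias unchanged and make the rise in type I error smaller. The case for adjustment is that a reader cannot at present rule the bias in or out. It does not rest on narrower intervals, which pack-years alone cannot be expected to give.

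**What to change.** 1. Report pack-years by S, Q and RS.
2. State which visit's smoking status defines the groups for each contrast.
3. Make the reported between-group effect an adjusted contrast. Model the change from baseline, or the follow-up value with baseline as a covariate, or use a mixed model over the three phases. Include smoking status, pack-years, medicine use and other baseline factors confirmed as collected (such as age, and sex if recorded). Name one of these models as the main one, because in non-randomised groups change scores and baseline-adjusted values need not agree.
4. Show the unadjusted result alongside, labelled descriptive.

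**Cost.** A little more analysis work, a few degrees of freedom out of 108 participants, and some overlap between age and pack-years. The plan already names R and JMP Pro, and pack-years need no new data. The Statistical Analysis section is written in the past tense, so this may mean a reanalysis and should then be labelled as one. The change does not extend to the retrospective arm, where no pack-years measure is described.

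### The retrospective pre/post contrast uses only patients with a file test in both years; if high first values prompted retesting, regression to the mean could pass for an effect of cessation

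*Combined protocol and SAP*

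**What the plan says.** Under Retrospective Arm, Study design, the data are described thus: "Two blood test results, as documented in medical files, were collected and analyzed". The baseline result is "The first one during the year preceding the smoking cessation workshops" and the follow-up result is "the second during the year after completing them". Both come from existing records. No study visit generates them, unlike the prospective arm, which measures at fixed time points.

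The stated sample is 200 patients. The exclusions are benign tumors, bariatric procedures, and patients who could not be reached by telephone. A missing blood test is not among them. The plan gives no count of attendees with no test, one test or two, and does not say whether having both was an entry condition.

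The Statistical Analysis section fixes the contrast: "Each patient constituted his own control – each post workshop result was compared with the pre workshop result". Patients are also classified as smokers (S) or quitters (Q), and tests for unmatched groups are listed. However, no test of change between Q and S is named, and no adjustment for the baseline value is mentioned.

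**The concern.** A within-patient comparison needs two values, so the analysed patients are those for whom someone ordered a test in both years. If the second order depended on the first result, the retested group would over-represent high first values, some of them high by chance or short-term variation. Those values drift back towards the patient's usual level on retest. A paired t-test or a Wilcoxon signed rank test reads that drift as change.

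Comparing each patient with himself removes stable differences between patients. It does not remove this effect, because the selection acts on the first of the two values being compared.

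At stake is the arm's main message. A fall in glucose, TC, LDL or TG could be credited to stopping smoking when nothing changed, or a true worsening after quitting could be masked. The prospective arm is not affected by this mechanism.

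**Working it through.** The plan gives no effect size, SD, retest rate or derivation of the 200, so there is no figure of its own to reproduce. The calculation below is an illustration.

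**From the documents:** two-sided alpha 0.05; n=200.

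**Assumed:** standardised normal baseline; no true change; pre/post correlation rho = 0.7; retest probability pH above a cut-off c (in SD) and pL below it; selection acts on the measured first value.

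**Formulas**, with f = 1 − Φ(c) and φ(c) the normal density at c:
- Proportion retested: P = f·pH + (1 − f)·pL
- Baseline shift of the retested: m = (pH − pL)·φ(c)/P
- Expected change: d = −(1 − rho)·m
- Baseline variance of the retested: v = [pH(f + cφ) + pL(1 − f − cφ)]/P − m²
- SD of change: s = √[(1 − rho)²·v + 1 − rho²]
- Rejection rate: Φ(−1.96 − k) + Φ(−1.96 + k), with k = |d|√n/s

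**Worked case, 0.8 v 0.5 above +1 SD.** f = 0.1587 and φ = 0.2420. P = 0.1587×0.8 + 0.8413×0.5 = 0.5476. m = 0.3×0.2420/0.5476 = 0.133. d = −0.3×0.133 = −0.040. v = 1.115, so s = 0.781. k = 0.0398×14.14/0.781 = 0.72, giving 11%.

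| Retest probability | m (SD) | d (SD) | s | k, n=200 | Rejects, n=200 |
|---|---|---|---|---|---|
| 0.8 v 0.5 above +1 SD | 0.133 | −0.040 | 0.781 | 0.72 | 11% |
| 0.9 v 0.5 above +1 SD | 0.172 | −0.052 | 0.783 | 0.93 | 15% |
| 0.9 v 0.4 above +0.5 SD | 0.318 | −0.095 | 0.778 | 1.73 | 41% |
| equal above and below | 0 | 0 | 0.775 | 0 | 5% |

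With an assumed LDL SD of 35 mg/dL, the three falls are 1.4, 1.8 and 3.3 mg/dL.

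**Smaller group.** The split between Q and S is not given, so a test within quitters would have fewer than 200 patients. At an illustrative n=60 the first two cases reject about 7-8% of the time. In the third, k = 0.0953×7.75/0.778 = 0.95, giving about 16%.

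**Wider range at n=200**, with rho 0.6-0.9 and 20-40% of first values counted as high: 0.8 v 0.6 gives 6-11%; 0.8 v 0.4 gives 11-42%.

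**Quitters against smokers.** If both groups have the same baseline and the same retesting, d is equal in both and cancels in the difference. If retested quitters started, say, 0.5 SD higher on the measured value, unadjusted changes would differ by 0.3×0.5 = 0.15 SD with no true effect. Given the measured baseline, the expected follow-up value is 0.7 × baseline in both groups, so the baseline-adjusted difference is 0.

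**The case against.** The strongest objection is that the documents give no reason for any test. Annual checks or routine monitoring fit the text as well as result-driven retesting does. Requiring two tests does not in itself cause regression to the mean: when retesting is unrelated to the first value, the bias is exactly zero. This objection stands. A reader might infer that retesting was driven by abnormal results; the documents neither say so nor rule it out.

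Three further limits also stand:
- A raised baseline among the retested is not proof of bias. If retesting follows a persistent trait, such as a known diagnosis under regular monitoring, the baseline is raised but no such fall need follow. The product of shift and (1 − rho) applies only when selection acts on the measured first value.
- One decision to retest cannot be driven fully by every analyte. A retest prompted by LDL shifts glucose only as far as the two are correlated, so the tabulated falls should not be assumed for all outcomes at once.
- Smokers from the same workshops would regress too. A reader might infer that the bias survives a Q-versus-S comparison because abnormal results also prompt quitting, but the documents contain nothing to support that second assumption.

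The objection does not remove the gap in the plan. The cancellation between Q and S helps only if that comparison is made, and the contrast actually specified is the unprotected one.

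**Conclusion.** The concern holds as a conditional one. As written, the plan lets a within-patient change among patients with two file tests be read as an effect of cessation, without safeguarding against regression to the mean and without reporting how the pairs arose. Whether any bias exists cannot be determined from the documents.

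If second tests were ordered more often because the first value was high, the illustrated bias is small in SD units. It can still raise the 5% error rate appreciably at n=200: roughly double to triple in the milder cases tabulated, and about eightfold in the stronger one. These figures rest on the assumed correlation and retest rates and on selection acting on the measured first value. They are not estimates for this cohort.

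**What to change.** **Main change, using data already collected.** Define the retrospective cessation effect as the Q-versus-S difference in follow-up value adjusted for the baseline value (ANCOVA), with an interval, for each analyte. Report the within-quitter pre/post change descriptively, and do not credit it alone to cessation. This removes the bias when retesting and quitting depend on the measured baseline. It does not remove confounding, since quitting was not randomised.

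**Sensitivity analysis, at the cost of one extra record pull and wider intervals:**
- Report how many 2014 attendees had 0, 1 and 2 tests, by smoking status where it is known (status came from the telephone call).
- Compare first values of those with and without a second test.
- Model having a second test on the first value, age, sex and other file variables, and show the inverse-probability-weighted change beside the unweighted one.

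State that weighting corrects only for recorded variables, leaves selection into having a first test untouched, and refers to all attendees with a first test. Because it changes the target population, a fall that disappears on weighting is a warning and not proof that the fall was spurious. It should not be used as an automatic decision rule.

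### The plan names pooled-variance tests for unmatched smoking-status comparisons; Welch's versions would protect the stated 5% level at almost no cost (cheap improvement, low priority)

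*Combined protocol and SAP*

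**What the plan says.** The Statistical Analysis section gives one rule for normally distributed data: "To determine significant statistical differences between two sets of data with normal distribution we used Student's t-test/ ANOVA". The rule does not separate paired from unpaired use, and it mentions neither a check of variances nor an unequal-variance version. For data that may not be normal, paired sets go to the Wilcoxon signed rank test, and "for unmatched sets-, the Mann Whitney's u-test was used". The threshold is common to all tests: "P<0.05 was considered significant" and "All statistical tests were two tailed".

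The only comparison written out is within-patient: "Each patient constituted his own control – each post workshop result was compared with the pre workshop result".

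Groups are formed by observed smoking status. In the prospective arm (Anthropometric measurements) participants are smokers, quitters or relapsers, "based on self-reported data at each visit". In the retrospective arm (Study design), "Participants were classified as smokers (S) and quitters (Q"), with status checked by telephone. On numbers, "The prospective arm included 108 participants aged 30-70", and the retrospective arm reviewed 200 files. No counts or SDs by smoking status are given.

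**The concern.** Student's t-test and classical ANOVA estimate one common variance. They hold their nominal level when the true variances are equal, and the two-group test also holds it closely when the groups are of equal size. Nothing in this design secures either condition for a comparison by smoking status: the sizes follow from who quits and who relapses, and the plan gives no reason to expect equal spread.

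If the smaller group is the more variable one, the pooled standard error is too small and false positives exceed 5%. If the larger group is the more variable one, the standard error is too large and power is lost. What is at stake is the calibration of any between-status P value for weight, BMI, waist, WHR, glucose or lipids. Those contrasts matter because a pre-to-post change alone does not separate quitting from the passage of time or workshop attendance.

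**Working it through.** **Inputs from the documents.** Two-sided level 0.05; N = 108 (prospective) and N = 200 (retrospective).

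**Assumed, because the documents are silent.** Share of quitters, and r = SD in quitters / SD in smokers, taken as 1 to 2. The smoker SD is set to 1, and the true means are equal.

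**Formulas for the pooled t-test.**
- Expected pooled variance: sp² = [(nS − 1) + (nQ − 1)r²] / (N − 2)
- Variance the test uses: E = sp²(1/nS + 1/nQ)
- True variance of the difference in means: V = 1/nS + r²/nQ
- Large-sample two-sided error: 2[1 − Φ(1.96·√(E/V))]

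**Reproducing the stated 5%.** With r = 1, E = V, so the error is 5.0% at every split. Simulation with r = 1 gives 4.8-5.2%.

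**Three worked cells, N = 108, r = 2.**
- 27 quitters, 81 smokers: sp² = (80 + 26×4)/106 = 1.736; E = 0.0857; V = 1/81 + 4/27 = 0.1605; √(E/V) = 0.731; error = 15.2%.
- 54 and 54: sp² = (53 + 53×4)/106 = 2.5; E = V = 0.0926; error = 5.0%.
- 81 quitters, 27 smokers: sp² = (26 + 80×4)/106 = 3.264; E = 0.1612; V = 1/27 + 4/81 = 0.0864; √(E/V) = 1.366; error = 0.7%.

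**Student's t, same formula, N = 108.**

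| Quitters / smokers | r = 1.25 | r = 1.5 | r = 2 |
|---|---|---|---|
| 27 / 81 (25%) | 8.0% | 10.8% | 15.2% |
| 36 / 72 (33%) | 6.9% | 8.5% | 11.0% |
| 54 / 54 (50%) | 5.0% | 5.0% | 5.0% |
| 72 / 36 (67%) | 3.5% | 2.6% | 1.6% |
| 81 / 27 (75%) | 2.9% | 1.7% | 0.7% |

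**Simulation, normal data, equal means, 40,000 replicates per cell, N = 108.** Each entry gives r = 1.25, then 1.5, then 2.

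| Quitters / smokers | Student | Mann-Whitney | Welch |
|---|---|---|---|
| 32 / 76 (30%) | 7.0, 9.5, 12.6% | 5.9, 7.3, 9.1% | 4.7, 5.2, 5.0% |
| 54 / 54 (50%) | 5.0, 5.0, 5.2% | 5.0, 5.2, 5.8% | 5.0, 5.0, 5.1% |
| 76 / 32 (70%) | 3.1, 2.2, 1.3% | 3.8, 3.2, 2.8% | 4.8, 4.8, 5.0% |

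A larger N does not help. At N = 200 with 60 quitters and 140 smokers, Student gives 7.5, 9.3 and 12.5%. With 140 and 60 it gives 3.3, 2.4 and 1.2%. Over all two-group cells (both N, quitter share 20-80%, r from 1 to 2) Welch stayed at 4.7-5.2%.

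**Three groups, N = 108, only quitters more variable (r = 1.5, then 2).** Classical ANOVA with S/Q/RS = 54/32/22 gives 6.0 and 7.3%; 22/64/22 gives 1.7 and 0.9%; 36/36/36 gives 5.1 and 5.8%. Welch's ANOVA gave 4.9-5.1% in the four three-group cells in which it was run.

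**Paired comparison.** With post-to-pre SD ratios of 1 to 2 and 32 or 54 pairs, the paired t-test gives 4.8-5.3%.

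**Power.** With equal variances, Student against Welch is 80.4% v 79.3% (27/81), 80.5% v 80.0% (36/72), and no different at 54/54. With 72 quitters and 36 smokers, a difference that Welch detects with 80% power is detected by Student with 72% (r = 1.5) or 66% (r = 2).

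**The case against.** The strongest reply is that the harm needs two conditions together, unequal sizes and unequal spreads, and the documents show neither. No passage says that quitting widens the spread of weight change, and nothing bears on the spread of glucose or lipids, which are all that the retrospective arm measures. The one comparison spelled out is within-patient, and the sentence naming Student's test can be read as covering paired use, where equal group variances are not needed. The advice to prefer Welch could be given to almost any plan that names a t-test. The text also does not show which option was run in JMP or R.

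Most of this stands, and it limits the point. A reader might infer that the 5% rule fails for every unmatched comparison, or that greater spread among quitters is enough to inflate false positives. The documents do not support either reading. At an even split Student's test holds 5% whatever the SD ratio, and if the more variable quitters are the majority the test is conservative. Nor should a reader infer that the pre-post results are miscalibrated, or that Mann-Whitney fails as badly as Student: its departures are clearly smaller. The plan mentions no confidence intervals for group differences and no regression, so there is nothing to criticise on those.

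What the reply does not remove is that the plan provides a test for unmatched sets and classifies both arms by smoking status, so between-status tests are implied. As written, those on normal data use a pooled variance with no safeguard. If Welch was used in practice, the text should say so.

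**Conclusion.** The point holds as a conditional one. For unmatched smoking-status comparisons of normally distributed outcomes, the 5% level is not guaranteed, because group sizes are not fixed by design and the named tests assume equal variances. Whether it is missed here, in which direction and by how much cannot be established without group sizes and SDs.

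The range of about 7-15% (quitters 25-33% of 108) down to about 1-4% (quitters 67-75%) rests on three assumptions: an SD ratio of 1.25 to 2 with quitters the more variable, normal data, and those splits. If smokers were the more variable group, the directions would reverse. The within-patient comparisons stand as planned. This is a cheap improvement of low priority.

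**What to change.** In the Statistical Analysis section, state that unmatched comparisons of normally distributed outcomes by smoking status use Welch's t-test for two groups and Welch's ANOVA for three. Re-run those comparisons in R, which the plan already names. Keep the paired tests, and Mann-Whitney for unmatched non-normal data, as planned. Reporting the count and SD in each smoking-status group alongside the results would let readers judge how much the choice matters.

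The cost is one sentence, a re-run, and about one percentage point of power or less if the variances are in fact equal.

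### The only contrast the statistical section defines is post versus pre within each patient; no quitter-versus-smoker comparison is specified, so the test of cessation cannot be identified

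*Combined protocol and SAP*

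**What the plan says.** The title poses a question about the short-term effect of stopping smoking. Under STATISTICAL ANALYSIS, the one comparison spelled out is "Each patient constituted his own control – each post workshop result was compared with the pre workshop result". That sentence does not say whether it applies to all participants or within each status group, nor which of phases 1 and 2 is the post value in the prospective arm.

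The same section names tests that can compare independent groups. A t-test/ANOVA is given "To determine significant statistical differences between two sets of data with normal distribution", without saying whether it is paired. It adds that "for unmatched sets-, the Mann Whitney's u-test was used", and lists Fisher's test for proportions. None of these is tied to named groups or to an outcome.

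Status appears elsewhere. The prospective arm (Anthropometric measurements) classifies smokers, quitters and relapsers by self-report at each visit. The retrospective arm (Study design) classifies smokers and quitters, with status checked by telephone. Both arms also look at cessation medicines; the retrospective text reads "The effect of smoking cessation medications on metabolic profile was also examined".

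On timing, the retrospective blood tests are "The first one during the year preceding the smoking cessation workshops" "and the second during the year after completing them". The prospective measurements are at the third weekly meeting, the eighth, and 6 months after the program.

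**The concern.** A change from before to after the workshop in quitters is the sum of any effect of stopping and whatever would have changed anyway in people attending the same workshops: season, workshop advice, and ageing where the interval is long. The own-control rule removes stable differences between patients but not these shared changes. If it is the test of cessation, a significant result in quitters can arise with no cessation effect.

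Smokers who attended the same workshops are the natural comparator, and they are already classified. A reader cannot tell from the plan whether they were used, at which visit status was fixed, where relapsers went, or whether follow-up values or changes were compared.

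**Working it through.** The plan gives no figure to reproduce: no sample-size calculation, SD, drift or quit split. The check is mainly textual. All arithmetic beyond step 2 rests on assumptions, named where they enter.

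**1. What could the unmatched sets be?** The text offers at least two candidates: quitters versus smokers, and medication users versus non-users. Both are mentioned and neither is assigned to a test. Naming a test does not define a contrast.

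**2. How much time is there for shared change?**
- Prospective, phase 0 to phase 1: 8 − 3 = 5 weeks. Phase 2 falls 6 months after the program.
- Retrospective: up to 12 + 12 = 24 months, plus the workshop. The interval also varies between patients.

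**3. Can separate pre/post tests in each group stand in for a direct comparison?** Suppose quitters and smokers change equally, by d = 0.2 SD of change, with an even split (assumed). Two-sided power at 0.05 is approximately 1 − Φ(1.96 − d√n).
- n = 54 per group: 0.2 × √54 = 1.47, power 0.312. The chance that exactly one group is significant is 2 × 0.312 × 0.688 = 0.43.
- n = 100 per group: 0.2 × √100 = 2.00, power 0.516. The chance is 2 × 0.516 × 0.484 = 0.50.

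Over d = 0.1 to 0.3 and quitter shares of 30% to 70%, the chance is about 0.20 to 0.55 (N = 108) and 0.25 to 0.55 (N = 200). Significance in quitters but not in smokers is therefore no evidence of a difference.

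**4. Effect of drift on the pre/post test (illustrative).** With no cessation effect and shared drift of 0.05 / 0.1 / 0.2 SD of change, a paired t-test (non-centrality d√n) rejects as follows:
- 60 quitters: 0.07 / 0.12 / 0.33.
- 120 quitters: 0.08 / 0.19 / 0.58.

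At 0.05 SD the inflation is small. Nothing in the documents supports 0.2 SD over 5 weeks.

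**5. What a between-group test does not cure (illustrative).** It removes drift common to both groups, not self-selection. A non-causal shift between groups of 0.05 / 0.1 / 0.2 SD of change gives rejection of 0.06 / 0.08 / 0.18 (60 vs 48) and 0.06 / 0.11 / 0.28 (120 vs 80).

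**6. Change score or baseline adjustment?** Assume a stable baseline gap g between the groups (in SD of the outcome), pre/post correlation r = 0.7, and no effect. The change-score difference is then centred on zero. The baseline-adjusted difference is biased by g(1 − r), with standard error about √(1 − r²) × √(1/a + 1/b) × √(1 + g²p(1 − p)), where p = a/(a + b).
- 60 vs 48: g = 0.2 gives 0.06/0.139 = 0.43, rejection 0.07; g = 0.5 gives 0.15/0.142 = 1.05, rejection 0.18.
- 120 vs 80: g = 0.2 gives 0.06/0.104 = 0.58, rejection 0.09; g = 0.5 gives 0.15/0.106 = 1.41, rejection 0.29.

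Simulation agrees closely, with the change-score test staying near 0.05. If the groups would instead regress to a common mean, baseline adjustment is the better choice. Neither analysis is safe alone.

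**7. Precision.** Detectable difference at 80% power, in SD of change, is about (1.960 + 0.842) × √(1/a + 1/b) between groups, and 2.802/√a for pre/post in a quitters. For 54 vs 54 these are 0.539 and 0.381. The t-based values are:

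| Quitters vs smokers (assumed) | Between groups | Pre/post in quitters |
|---|---|---|
| 54 vs 54 | 0.54 | 0.39 |
| 32 vs 76 | 0.60 | 0.51 |
| 100 vs 100 | 0.40 | 0.28 |
| 60 vs 140 | 0.43 | 0.37 |

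Setting relapsers apart would raise the prospective figures; 40 vs 40 gives 0.63.

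**The case against.** The strongest reply is that the own-control sentence merely explains what the paired tests are for. It follows directly on the list of paired and unmatched tests, and the most natural use of status groups together with unmatched tests is a comparison by status. On that reading the plan is under-described and no wrong analysis has been shown. Nor do the documents state a formal hypothesis or primary outcome, so the title alone does not settle which contrast was primary.

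Most of this stands. A reader might infer that quitters and smokers were never compared, or that the pre/post test was certainly taken as proof of a cessation effect. The documents support neither: the listed tests leave room for the comparison, and the data to make it were collected. What survives is that the only contrast stated is the one that cannot isolate cessation, and that nothing in the text assigns the groups to any other.

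It is also fair to object that the drift figures are wholly assumed, and that prescribing a baseline-adjusted regression alone would be unsafe with self-selected groups. Both objections are accepted: the drift figures carry no weight in the conclusion, and step 6 is why the fix asks for both analyses.

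**Conclusion.** The point holds as a gap in specification with a real consequence. As written, the test that answers the title question cannot be identified or reproduced, and the one contrast that is defined mixes cessation with change common to all attendees. The concern is strongest in the retrospective arm, with its interval of up to about 24 months plus the workshop, and weak for phase 0 to phase 1. Confidence is high on the missing text and lower on the harm, which arises only if the own-control rule was the test of cessation.

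A reader might take rejection rates such as 0.33 or 0.58 as the study's error rate. They are not: they follow from an assumed drift of 0.2 SD and assumed numbers of quitters. The study is not invalidated, since the groups and baseline values for a direct comparison exist. The change should be made because it answers the question better at modest cost.

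**What to change.** State that the test of cessation in each arm is the difference between quitters and smokers in change from baseline, reported with a 95% confidence interval, and name the outcome.

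- **Prospective arm:** analyse phase 1 and phase 2 separately, with status as classified at that visit and relapsers shown as their own group.
- **Retrospective arm:** take account of the months between the two tests, since unequal intervals would leave unequal drift in the two groups.
- **Both arms:** report a regression of the follow-up value on status and baseline beside the change comparison, and discuss any disagreement. Adjustment for age, cessation-medication use and, in the prospective arm, pack-years can be added as supporting analysis.
- Keep the pre/post tests as descriptive. State as a limitation that confounding from self-selected, self-reported status remains.

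The cost is wording plus a re-analysis, because the plan describes the work as done ("Data was analyzed using JMP Pro 12 and R software"). The status groups and baseline values are already collected, and test dates should be in the files reviewed. Precision falls as in step 7, and some pre/post findings may not carry over to the direct comparison.
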